Visit 1 and Visit 2: Visit 1 is planned 12 months (Year 1) after the parent study last visit and Visit 2 is planned 24 months (Year 2) after the parent study last visit. The visits should be planned as close to the yearly date as possible, but as a maximum, fall within a window of ± 30 days. Visit 1 and 2 are planned relative to parent study last visit; therefore, participants with a gap period between the parent study last visit and extension Baseline will have less than 12 months between the extension Baseline and Visit 1 and less than 24 months between extension Baseline and Visit 2.

Early Withdrawal: In the event of early discontinuation from the extension study, the participants will be invited for an Early Withdrawal visit as soon as possible. Visit schedules for efficacy and safety assessments are detailed in the Schedule of Activities (Section 1.3). In case the participant is not willing or cannot return to the site for the Early Withdrawal visit, a telephone call will be organized to obtain the reason for withdrawal and AEs reporting.

Unscheduled visits: A participant may return for an unscheduled visit at the discretion of the Investigator and these visits may include assessments as described in the Schedule of Activities (Section 1.3). If a participant experiences a relapse requiring treatment with steroids or switching to other DMD, a blood sample will be taken before administration of these drugs, irrespective of

time left for the next scheduled visit and blood sample collection, and irrespective of participant continuing or discontinuing the study. Further assessments and management of relapse are at the discretion of the physician.

The data from scheduled and unscheduled visits will be collected in the electronic case report form (eCRF). The schema and visit schedules for efficacy and safety assessments are detailed in the study schema (Section 1.2) and the Schedule of Activities (Section 1.3).

The planned study duration for each participant is 2 years (see Section 1.2). The study aims to enroll the first patients in Q1 2021 and have the Last Patient Last Visit in Q4 2023.

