9.5 Time Window

- Day 1 is the day of start of study medication at MAGNIFY MS Baseline Visit, the day before is Day -1 (no Day 0 is defined).
- Study day is defined relative to Day 1.

The visit schedule in the Extension Study is defined as follows:

- 1 month = 30 days,
- 1 year = 360 days,

relative to the M24 Visit in the parent study.

- MAGNIFY Extension Baseline Visit: The visit is planned to coincide with or be as near to M24 as possible to minimize the transition gap period, it may also be the same visit as M24.
- Visit 1: 1 year ((360 days) after M24 Visit (\pm 30 days)
- Visit 2: 2 years (720 days) after M24 Visit (± 30 days)

Visit 1 and Visit 2 will also be referred to as the M36 Visit and the M48 Visit, respectively, in the following sections of this IAP as well as in the Tables, Listings, and Figures (TLF) outputs, for consistent presentation of analyses and results over time. Footnotes will be added in the TLF outputs to clarify that these Visits are to be understood as nominal Visits.

In each analysis, should an assessment be delayed, participants' assessment data will be treated as though it occurred at the nominal time point specified (i.e., data collected out of visit windows will not be excluded or adjusted in any analysis) and inferences will be conducted accordingly. Thus, further time windows will not be specified. The MRI assessment will be the only exception to this rule. Handling of out-of-window MRI assessments is discussed in Section 9.8.

All observations from unscheduled visits will be included only in the analyses of visit independent summaries (e.g., counts of AEs, concomitant medications and procedures, relapse reporting and EDSS) unless for the last assessment available. In this case the missing Early Withdrawal (EW) visit will be imputed by the unscheduled visit.

The assessments of the EW visit will be mapped to the nearest planned post-baseline visit with a missing assessment before or after the EW visit of the individual assessment for all statistical analyses and descriptive summaries. As not all assessments of the EW are performed at each visit, the different assessments of the EW can be assigned to different visits. If the duration (in days) between the EW visits and two missing planned visits are equal, then the assessment will be assigned to the later visit.

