The 6MCDP during Extension Study Period is defined as sustained increase in EDSS score that started during the Period. A Sustained Increase in EDSS score is defined by an increase of:

- at least 1.5 points if the Baseline EDSS score was 0, or
- at least 1 point if Baseline EDSS score was between 0.5 and 4.5 inclusively, or
- at least 0.5 point if the Baseline EDSS score was at least 5,

that occurs over a 6-months' time-period.

The increase will be defined as sustained when it occurs on two post-Baseline Visits during the Extension Study Period that are at least 166 days apart (to be consistent with the parent study minimum visit gap) and no observations at any other visits (including unscheduled visits) in between are less than the defined increase. The assessment date of the earlier of the two EDSS assessments with the defined increase will be defined as the start date of 6MCDP.

For descriptive summaries the following rules will be defined:

Qualifying Relapse

- Yes: any qualifying relapse reported during the Extension Study Period,
- No: Extension study period completed, and no qualifying relapse reported during the Extension Study Period,
- Unknown: otherwise.

6MCDP

• Yes: sustained increase in EDSS score that started during the Extension Study Period,

- No: at least 2 post-Baseline EDSS assessments that are 166 (or more) apart and no sustained EDSS progression that started during the Extension Study Period,
- Unknown: Otherwise.

MRI activity

- Yes: any T1-Gd+ or active T2 observed during the Extension Study Period,
- No: at least one post-Baseline MRI and no T1-Gd+ or active T2 observed during the Extension Study Period,
- Unknown: otherwise.

Analysis (Analysis Set)	Derivation	Statistical Analysis Methods	Missing data handling		
	Primary endpoint: Proportion of participants with NEDA-3 during Year 3 Visit and Year 4 Visit Period after the initial dose of cladribine tablets				

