14.2.3 Time to MRI Activities, 6MCDP, Qualifying Relapse and Treatment Start with Other DMDs

Time (in months) from the initial dose of cladribine tablets (i.e. start date = date of Day 1 as defined in Section 9.5) to the following events will be calculated as [event date or censoring date as applicable – start date + 1]/30.4375, and analyzed similarly as in Section 14.2.2 using the KM method.

- first new or enlarging T2 lesion
 - Event date: the scan date of the first MRI during the Parent and Extension Study Period where at least one active T2 lesion (see Section 9.8 for definition) is identified
 - Censoring date: participants with no active T2 lesion identified at any scans during the Parent and Extension Study Period will be censored at the scan date of the last available MRI during this Period
- first new T1 Gd+ lesion
 - Event date: the scan date of the first MRI during the Parent and Extension Study Period where at least one new T1 Gd+ lesion (see Section 9.8 for definition) is identified
 - Censoring date: participants with no new T1 Gd+ lesion identified at any scans during the Parent and Extension Study Period will be censored at the scan date of the last available MRI during this Period
- first 6MCDP, as measured by EDSS
 - Event date: the start date of the first 6MCDP during the Parent and Extension Study Period
 - 6MCDP during the Parent and Extension Study Period will be defined similarly as in Section 14.1.1 with just Extension Study Period replaced by Parent and Extension Study Period.
 - Censoring date: participants with no 6MCDP started during the Parent and Extension Study Period will be censored at the assessment date of the last available EDSS during this Period
- first qualifying relapse
 - Event date: the onset date of the first qualifying relapse during the Parent and Extension Study Period

 Censoring date: participants with no qualifying relapse reported during the Parent and Extension Study Period will be censored at the Extension Study completion/discontinuation date

Time (in months) from M24 Visit (i.e. start date = end date of M24 Visit + 1) to the following events will be calculated as (event date or censoring date as applicable – start date + 1/30.4375, and analyzed similarly as in Section 14.2.2 using the KM method.

- first new or enlarging T2 lesion
 - Event date: the scan date of the first MRI during the Extension Study Period where at least one active T2 lesion (see Section 9.8 for definition) is identified

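### The Day 1 curve for time to first 6MCDP joins two EDSS schedules: rises first seen at M24 or M36 need about 10-14 months to be confirmed at scheduled visits, so part of any slowing after M24 may be an artefact

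*SAP*

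**What the plan says.** SAP 14.2.3 carries the primary-endpoint definition of 6MCDP over to the whole four years: "6MCDP during the Parent and Extension Study Period will be defined similarly as in Section 14.1.1", with only the period changed. Under SAP 14.1.1 the two raised scores must be "at least 166 days apart (to be consistent with the parent study minimum visit gap", and the rise counts as sustained only if "no observations at any other visits (including unscheduled visits) in between are less than the defined increase". On dating, "The assessment date of the earlier of the two EDSS assessments with the defined increase will be defined as the start date of 6MCDP". For non-events, "participants with no 6MCDP started during the Parent and Extension Study Period will be censored at the assessment date of the last available EDSS" in the period.

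The extension schedule is yearly. Protocol 4.1 states that "Visit 1 is planned 12 months (Year 1) after the parent study last visit and Visit 2 is planned 24 months" after it, and that visits must "fall within a window of ± 30 days". SAP 9.5 puts Visit 1 at 360 days and gives "Visit 2: 2 years (720 days) after M24 Visit". The Schedule of Activities requires an unscheduled EDSS only when relapse is suspected. SAP 11.3 lists the Extension Baseline EDSS but still uses it for progression in participants who had a gap period.

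SAP Section 7 discloses the move from 3-month to 6-month confirmation. SAP 7 and 9.8 consider the longer spacing only for T1 Gd+ lesions, not for EDSS.

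**The concern.** A confirmation rule yields comparable events over time only if the visits that can confirm an event are equally spaced. Here the minimum interval matches the parent visits, but after M24 the next scheduled EDSS is about a year away. A rise that resolves after, say, nine months has some chance of being confirmed in the parent years and usually none at scheduled extension visits. Detection can also lag by up to 12 months.

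The study's purpose is the effect in Years 3 and 4, so a curve that flattens after M24 is what readers will look for. They could take it as durable benefit when part of it comes from the schedule. No analysis visible in the SAP uses a common EDSS schedule. The treatment-completer, DMD-subgroup and crude-percentage versions of the NEDA-3 analyses, and the subgroup version in 14.2.3, all keep the same rule.

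**Working it through.** **1. Visit gaps (Protocol 4.1, SAP 9.5; 30.4375 days per month, SAP 9.4)**

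- Rule minimum: 166 / 30.4375 = 5.45 months.
- M24 to M36: 360 ± 30 = 330 to 390 days = 10.8 to 12.8 months.
- M36 to M48: (720 − 30) − (360 + 30) = 300 days, up to (720 + 30) − (360 − 30) = 420 days, which is 9.9 to 13.8 months.

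The 166-day minimum therefore never binds between scheduled extension visits. The 166 days cannot be reproduced from these documents, because the parent EDSS schedule is not in them. It would equal 180 − 2×7 for 6-monthly visits with a 7-day window. That is an assumption, and the 6-month parent grid used below is inferred.

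**2. Closed form for transient rises**

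Let d be the detection interval, c the confirmation interval and m the mean duration (exponential), all in months. The chance that a transient rise is seen and confirmed is

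T(d,c) = [(1 − exp(−d/m)) / (d/m)] × exp(−c/m).

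With transient share p, the share of all rises counted is A = (1 − p) + p×T. The values of m and p are assumptions. For m = 9:

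| Where the rise is first seen | (d,c) | T | A, p = 0.3 | A, p = 0.5 |
|---|---|---|---|---|
| up to M18 | (6,6) | 0.375 | 0.812 | 0.687 |
| M24 | (6,12) | 0.192 | 0.758 | 0.596 |
| M36 | (12,12) | 0.146 | 0.744 | 0.573 |

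M0-24 contains three intervals of the first kind and one of the second:

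- p = 0.5: 0.75×0.687 + 0.25×0.596 = 0.664. M24-36 against M0-24 is 0.573/0.664 = 0.86, a 14% fall. Against rises seen up to M18 alone it is 0.573/0.687 = 0.83, a 17% fall.
- p = 0.3: 0.75×0.812 + 0.25×0.758 = 0.799, and 0.744/0.799 = 0.93, a 7% fall.
- p = 0: A = 1 throughout, so there is no fall from this source.

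**3. Simulation of the SAP 14.1.1 rule**

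Constant onset rate, 6-monthly parent EDSS, yearly extension EDSS, no dropout, no unscheduled or gap-period EDSS. Ratio of the M24-36 rate to the M0-24 rate:

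- All rises permanent: about 0.98. For example, 5.89 against 5.84 per 100 person-years at an onset rate of 0.06 per year.
- 30-50% transient: 0.82-0.89 in one set of runs (11-18% lower). A second set, with onset rates of 0.03, 0.06 and 0.10 per year and mean durations of 6 and 12 months, gave 0.83-0.94 (6-17% lower).

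A repeat at 0.06 per year, with mean durations of 6, 9 and 12 months, suggests why the two sets differ. If a new rise may follow a resolved one, the ratio is 0.85-0.93. If each participant can have only one onset, it is 0.83-0.91, and a few percent of that fall is depletion of participants still able to progress, not schedule.

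**4. Size on the curve**

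At 0.06 per year, half transient, mean 12 months, the Kaplan-Meier estimates are 0.918 (M24) and 0.885 (M36) as planned. With 6-monthly EDSS throughout they are 0.915 and 0.875. The difference at M36 is about one percentage point.

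**5. The last year**

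With scheduled visits only, a rise first seen at M48 cannot be confirmed, yet completers stay at risk to M48. The M36-48 rate is then 0.00. This is a separate effect, but it decides how the sensitivity version must be censored (see the fix).

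**The case against.** The strongest reply is that the fall is not shown to occur. If progression is permanent, a longer confirmation interval loses almost nothing in M24-36. The transient share and durations come from outside the documents, and so does the 6-month parent grid. The months listed for parent visits in the SAP relate to MRI scans, and SAP Section 7 says parent visits could slip by more than six months. All of this stands, so the size is conditional.

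Second, other EDSS can shorten confirmation. With M36 at day 360, an Extension Baseline EDSS up to 194 days after M24 lies at least 166 days before M36 (360 − 166 = 194). One at 166 days or later can confirm a rise seen at M24. An unscheduled EDSS can also start, confirm or break a sequence. This softens the effect and makes the interval differ between participants. It does not restore a common rule.

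Third, the study is exploratory and SAP 14.2.3 reports percentiles, not period rates. The low percentiles may fall in the parent years, and a separate curve from M24 does not mix the schedules. This limits the harm to misreading one curve.

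Three stronger readings are tempting and are not supported:

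- That the rate must fall after M24 by construction. From longer confirmation, it falls only as far as rises are transient.
- That confirmation length halves the rate. The planned ratio of M24-48 to M0-24 is 0.42-0.51 in the second set of runs, but this comes mainly from the empty last year. About 0.75 would remain even if the parent spacing continued to M48.
- That every 6-11 month rise counts in the parent years. On a 6-month grid the chance for a rise of length L is (L − 6)/6: none at 6 months and 50% at 9.

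The Day 1 NEDA-3 and first-activity curves contain the same component, but the effect there is not quantified and only the earliest of three event types counts.

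**Conclusion.** The mismatch is in the text. A rule set to the parent visit gap is applied to one curve whose later part has yearly scheduled EDSS, where confirmation takes about 10-14 months. The consequence is conditional. The apparent 6MCDP rate in M24-36 is about 11-18% below that in M0-24 if 30-50% of rises are transient (6-17% in the second set of runs), and about 2% below if all are permanent. This assumes a constant true onset rate, 6-monthly parent EDSS and scheduled visits only. A flatter curve after M24 is therefore not by itself evidence of slower progression, nor do the documents show that such flattening would be wholly artefact. No error rate is at stake. Label: cheap improvement.

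**What to change.** 1. Check the parent EDSS schedule in the parent analysis plan (MAGNIFY MS IAP version 3.0).
2. Add to SAP 14.2.3 a sensitivity version of the Day 1 CDP curve on a common yearly EDSS grid: Baseline, M12, M24, M36 and M48, with each rise confirmed at the next yearly visit.
3. In that version, censor non-events at the last EDSS that could still be confirmed (M36 for completers). Otherwise M36-48 has no possible events. In simulation the yearly grid alone restores the M24-36 to M0-24 ratio to 0.94-0.99 but leaves M24-48 to M0-24 at about 0.5. With the censoring change, the later-to-earlier ratio is 0.97-1.02. The censoring change without the yearly grid leaves 0.83-0.94 when 30-50% of rises are transient.
4. In the current version, footnote that extension-onset events at scheduled visits are confirmed at about 12 months, so a flatter curve after M24 does not by itself show slower progression.

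Cost: one extra derivation from EDSS data already held, and fewer parent-period events in the sensitivity version. For example, the M0-24 rate goes from 4.23 to 3.58 per 100 person-years at an onset rate of 0.06 per year with half of rises transient (mean 12 months), and does not change if all are permanent. The grid is nominal, so delayed parent visits will still make the true intervals vary.

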15.1 Adverse Events

The definition of AE has been described in Appendix 7 of the CSP. All analyses described in this Section will be based on reported AEs during the Extension Study Period.

SAEs and events of lymphopenia (also if not serious) with an onset date prior to the MAGNIFY MS exit date and are ongoing on the MAGNIFY MS Extension enrollment date will be recorded on the "Medical History" CRF. A listing comprising all ongoing SAEs and events of lymphopenia (also if not serious) from the MAGNIFY MS trial will be presented.

Each participant will be counted only once within each SOC or PT. If a participant experiences more than one AE within a SOC or PT for the same summary period, only the AE with the strongest relationship or the worst severity, as appropriate, will be included in the summaries of relationship and severity.

Incomplete AE-associated dates will be imputed as described in Section 9.7.

15.1.1 All Adverse Events

All AEs reported during the Extension Study Period will be summarized using MedDRA (latest version available) PT as event category and MedDRA primary SOC body term as Body System category overall and by DMD subgroups as defined in Section 8.2.

Unless otherwise stated, adverse events will be displayed in terms of frequency tables: PT and primary SOC in alphabetical order.

Adverse events related to study treatment are those events with relationship missing, unknown or related.

The following overall frequencies of participants with the corresponding AEs will be prepared. In addition, the tables will be provided by PT and primary SOC in alphabetical order:

- Any AE,
- Any study treatment related AEs,
- Any serious AEs,
- Any non-serious AEs,

- Any study treatment related serious AEs,
- Any AE by severity (mild, moderate, severe),
- Any study treatment related AE by severity (mild, moderate, severe),
- Any AEs leading to death (AEs with outcome "fatal"),
- Any study treatment related AEs leading to death (AEs with outcome "fatal").
- Any AEs leading to study discontinuation,
- Any study treatment related AEs leading to study discontinuation.

Summary table for non-SAEs applying frequency threshold of 5% will be provided by SOC and PT.

Summary tables for serious and non-SAEs applying frequency threshold of 5% sorted by decreasing frequency will be provided by PT.

All AEs by worst severity will be presented by SOC and PT. Missing severity will be presented in all severity groups.

All AEs collected during the Extension Study Period will be listed by participant for the SAF.

Exposure Adjusted Incidence Rate

Exposure adjusted incidence rates (EAIR) are calculated as number of participants with AE divided by the total time at risk, which is defined as a sum of the individual times in years of all participants in the safety population from start of Extension Study Period to first onset of AE or end of the Extension Study Period, whichever occurs first.

The exact Poisson 95% confidence intervals for the EAIR are calculated using the relationship between the Poisson and the Chi-square distribution (Ulm, 1990):

$$LCI = \frac{\chi_{2n,\frac{a}{2}}^2}{2 \times t},$$

$$UCI = \frac{\chi_{2(n+1), 1 - \frac{a}{2}}^2}{2 \times t},$$

where t is the sum of the individual times in years of all participants and n is the number of participants with a specific AE for the EAIR, which will be the basis for the number of the degrees of freedom for the chi-square quantile for the upper tail probability χ^2 .

The incidence rate multiplied with 100 would give the number of AEs expected in 100 participants within 1 year.

EAIR of AEs will be presented overall, and by SOC and PT.

The following table will be provided:

• Exposure adjusted incidence rates of AEs by SOC and PT.

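### SAP 15.1.1 describes 100 × EAIR as a number of AEs, but the rate it defines counts participants with a first AE per 100 participant-years at risk

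*SAP*

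**What the plan says.** All of this stands in SAP Section 15.1.1, under Exposure Adjusted Incidence Rate.

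- **Definition.** The rate is "calculated as number of participants with AE divided by the total time at risk". Each participant's time runs "from start of Extension Study Period to first onset of AE or end of the Extension Study Period, whichever occurs first".
- **Inputs to the interval.** In the interval formulas "n is the number of participants with a specific AE for the EAIR", and "t is the sum of the individual times in years of all participants".
- **Interpretation.** "The incidence rate multiplied with 100 would give the number of AEs expected in 100 participants within 1 year".
- **Interval.** "The exact Poisson 95% confidence intervals for the EAIR are calculated using the relationship between the Poisson and the Chi-square distribution". The lower limit is the chi-square quantile with 2n degrees of freedom and subscript a/2, divided by 2t. The upper limit is the quantile with 2(n+1) degrees of freedom and subscript 1 − a/2, divided by 2t. The explanatory text mentions "degrees of freedom for the chi-square quantile for the upper tail probability".

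The EAIR is to be presented overall, by SOC and by PT. SAP Section 15.1 counts each participant once within a SOC or PT.

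**The concern.** The definition and the interpretation describe different quantities. The definition gives a first-event rate: a participant adds at most one to the numerator and leaves the risk set at that moment. The interpretation describes an event rate, in which every AE counts and all follow-up contributes.

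Long-term safety is a secondary objective (SAP Section 5), and no other AE rate in SAP Section 15 carries a confidence interval. The remaining summaries in 15.1.1 are participant frequencies and a listing, and no rate of all AEs over follow-up is planned. If the sentence reaches a table footnote or the study report, readers will take a first-event rate for the AE burden. Where AEs repeat within participants, they will usually take that burden to be lower than it was.

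**Working it through.** **Inputs.** From SAP 15.1.1: the numerator, the time at risk and the interval formulas quoted above. From the Protocol synopsis: 2 years of follow-up and 200 to 220 evaluable participants. The documents give no AE counts, rates or participant-years, so every rate, n and t below is an assumption.

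**1. The plan's interval.** Read the subscripts as cumulative (lower-tail) probabilities with a = 0.05, and assume n = 10 and t = 450 years, a rate of 10/450 = 2.22 per 100 participant-years.

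- Lower limit = 9.59 / (2 × 450) = 1.07 per 100
- Upper limit = 36.78 / (2 × 450) = 4.09 per 100

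At eight values of n from 1 to 150, P(X ≥ n) at the lower limit and P(X ≤ n) at the upper limit were both 0.0250. The printed formulas give the exact Poisson 95% interval.

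**2. When the SAP's sentence is true.** Suppose every participant has AEs independently at the same constant rate λ over T = 2 years.

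- Expected numerator per participant = 1 − exp(−λT)
- Expected time at risk per participant = (1 − exp(−λT)) / λ
- EAIR = ratio of the two = λ

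With 220 participants and λ = 1 per year, 190.2 are expected to have an AE over 190.2 years at risk. Then 100 × EAIR = 100, equal to the true 100 AEs per 100 participant-years.

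**3. A small example where it is not.** Take 100 participants followed for 2 years. Forty have a first AE at 0.5 years and three AEs each; sixty have none.

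- 100 × EAIR = 100 × 40 / (40 × 0.5 + 60 × 2) = 100 × 40/140 = 28.6
- AEs per 100 participant-years = 100 × (40 × 3) / (100 × 2) = 60

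**4. Variation between participants.** Let individual AE rates follow a gamma distribution with mean m per year and shape k. The probability of no AE by time s is S(s) = (k / (k + m·s))^k, and the EAIR over 2 years is [1 − S(2)] divided by the integral of S from 0 to 2.

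With m = 1:

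- k = 0.5: 0.5528 / 1.2361 = 0.447
- k = 1: 0.6667 / 1.0986 = 0.607
- k = 2: 0.75 / 1 = 0.750

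With m = 0.05:

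- k = 0.5: 0.0871 / 1.9089 = 0.0456
- k = 2: 0.0930 / 1.9048 = 0.0488

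| True AEs per 100 participant-years | 100 × EAIR, k = 0.5 | k = 1 | k = 2 |
|---|---|---|---|
| 100 | 44.7 | 60.7 | 75.0 |
| 20 | 14.9 | 17.0 | 18.3 |
| 5 | 4.6 | 4.8 | 4.9 |

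At a true 100, the SAP's reading understates the AE rate by 25% to 55%. At a true 5 the gap is 0.1 to 0.4 per 100 participant-years.

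**The case against.** **The definition is clear and the calculation is safe.** The numerator, the stopping of time at first onset and the meaning of n are all explicit, so a programmer would not derive a different EAIR. This stands: the fault lies in the interpretation only.

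**The sentence is right under a homogeneous Poisson model, and the planned interval is itself Poisson.** Step 2 confirms the first part. But an interval for the number of first events needs no assumption about recurrence, and the SAP states none. The interpretation therefore rests on a condition that the plan does not set out.

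**The size is assumed, and the table is descriptive.** The gamma shapes and mean rates have no source in the documents. The study is single-arm and tests no formal hypothesis (Protocol 9.1), Protocol 9.4.2 does not mention the EAIR, and the AE listing will show repeats. All of this stands and limits the consequence to how the table is read.

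Two stronger readings are tempting, and the documents do not support them.

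- *That the confidence limits are reversed.* If the upper-tail phrase is applied to both subscripts, n = 10 and t = 450 give a lower limit of 34.17/900 = 3.80 and an upper limit of 10.98/900 = 1.22 per 100. But the text never says that a/2 and 1 − a/2 are upper-tail areas. The phrase sits in a sentence about degrees of freedom, the method is named as exact Poisson, and the formulas are standard under cumulative notation. Reversed limits would also be visible in any output.
- *That the sentence overstates the share of participants affected in a year.* If 60% have an AE in 2 years at constant hazard, 100 × EAIR = 100 × (−ln 0.4)/2 = 45.8, while 100 × (1 − exp(−0.458)) = 36.8 per 100 are affected within one year. The SAP sentence speaks of AEs, not of participants affected, so this comparison answers a claim that the SAP does not make.

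**Conclusion.** The point holds for the interpretation sentence. As defined, 100 × EAIR is the number of participants with a first event per 100 participant-years at risk. It equals the AE rate when AEs recur independently at one constant rate common to all participants, and in general not otherwise.

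Under the assumed gamma shapes, the discrepancy is large for any AE and frequent SOCs and negligible for rare PTs. These figures show how the gap depends on frequency and do not predict this study's results. The EAIR values and the interval formulas are sound. What changes is what the rates may be said to show.

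**What to change.** 1. In SAP 15.1.1, replace the interpretation sentence, and any table footnote that uses it, with: *100 × EAIR is the number of participants with a first event per 100 participant-years at risk.*
2. Only if an AE count per 100 participant-years is to be reported, define it separately as all AEs divided by total follow-up time, without stopping at first onset.
3. As a minor clarification, state that the chi-square subscripts are cumulative (lower-tail) probabilities. The formulas stay as printed.

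Items 1 and 3 cost a sentence each plus footnotes and need no reprogramming. Item 2 is optional and would add one derived rate from data already collected.
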